**10.1.2. Financial Disclosure**

Investigators and sub-investigators will provide the sponsor with sufficient, accurate financial information as requested to allow the sponsor to submit complete and accurate financial certification or disclosure statements to the appropriate regulatory authorities. Investigators are responsible for providing information on financial interests during the course of the study and for 1 year after completion of the study.

**10.1.3. Informed Consent Process**

- The investigator or his/her representative will explain the nature of the study to the participant or his/her LAR and answer all questions regarding the study.
- Participants must be informed that their participation is voluntary. Participants or their legally authorized representative will be required to sign a statement of informed consent that meets the requirements of 21 CFR 50, local regulations, ICH guidelines, Health Insurance Portability and Accountability Act (HIPAA) requirements, where applicable, and the IRB/IEC or study center.
- The medical record must include a statement that written informed consent was obtained before the participant was enrolled in the study and the date the written consent was obtained. The authorized person obtaining the informed consent must also sign the ICF.
- Participants must be re-consented to the most current version of the ICF(s) during their participation in the study.
- A copy of the ICF(s) must be provided to the participant or the participant's legally authorized representative.

A participant who is rescreened is not required to sign another ICF if the rescreening occurs within 45 days from the previous ICF signature date.

GSK (alone or working with others) may use participant's coded study data and samples and other information to carry out this study; understand the results of this study; learn more about GSK3965193 and/or bepirovirsen or about the study disease; publish the results of these research efforts; work with government agencies or insurers to have the GSK3965193 and/or bepirovirsen approved for medical use or approved for payment coverage.

Sample testing will be done in accordance with the recorded consent of the individual participant/LAR(s).

By default, collected samples for the study will be stored for a maximum of 20 years. This storage period begins when the last participant completes the last study visit. This timeline can be adapted based on local laws, regulations or guidelines requiring different timeframes or procedures. In all cases, the storage period should be aligned with participant's consent. These additional requirements must be formally communicated to, discussed and agreed with GSK.

The ICF contains a separate section that addresses the use of participant data and remaining samples for optional further research. The investigator or authorised designee will inform each participant of the possibility of further research not related to the study/disease. Participants will be told that they are free to refuse to participate and may withdraw their consent at any time and for any reason during the storage period. A separate signature will be required to document a participant's agreement to allow any participant data and/or remaining leftover samples to be used for further research not related to the study/disease. Participants who decline further research will tick the corresponding “No” box.

#### **10.1.4. Data Protection**

- Participants will be assigned a unique identifier by the sponsor. Any participant records or datasets that are transferred to the sponsor will contain the identifier only; participant names or any information which would make the participant identifiable will not be transferred.
- The participant must be informed that his/her personal study-related data will be used by the sponsor in accordance with local data protection law. The level of disclosure must also be explained to the participant who will be required to give consent for their data to be used as described in the informed consent.
- The participant must be informed that his/her medical records may be examined by Clinical Quality Assurance auditors or other authorized personnel appointed by the sponsor, by appropriate IRB/IEC members, and by inspectors from regulatory authorities.
- The contract between sponsor and study sites specifies responsibilities of the parties related data protection, including handling of data security breaches and respective communication and cooperation of the parties.
- Information technology systems used to collect, process, and store study-related data are secured by technical and organizational security measures designed to protect such data against accidental or unlawful loss, alteration, or unauthorized disclosure or access.
- GSK has a global, internal policy that requires all GSK staff and complementary workers to report data incidents or breaches immediately, using dedicated tools. Clear procedures are defined for assessing and investigating data breaches to identify and to take appropriate remediation steps, to contain and to mitigate any risks for individuals resulting from a breach, in compliance with applicable laws.

#### **10.1.5. Committees Structure**

##### **10.1.5.1. Safety Data Review**

- An SRT is in place for each GSK product. It comprises a global cross-functional team responsible for the ongoing assessment of benefit-risk for a product. The SRT contributes to the continual assessment of incoming new efficacy and safety information.

- For Parts 1 and 2, participant safety will be monitored by members of the DEC, which is comprised of members of the study team and the Principal Investigator (or designate).
- For Part 3 and 4, participant safety will be continuously monitored by an internal SRT, which includes safety signal detection at any time during the study. Blinded data will be reviewed. The SRT will include a subset of the study team whose responsibility is to provide a forum for the proactive, aggregate, and holistic evaluation of the safety profile for the product over its lifecycle.
- In Parts 3 and 4 an IDMC will be involved in review of safety data as follows:
  - Part 3 – open-label bepirovirsen safety data will be reported to the IDMC once all participants who receive bepirovirsen have completed treatment. Unblinded safety data for GSK3965193 in Part 3 will also be shared with the IDMC for awareness prior to the start of Part 4.
  - Part 4 – the IDMC will provide full unblinded safety oversight.
- The IDMC will operate according to an IDMC charter.
- All safety data collected will be summarized and reviewed by the IDMC for agreement of next steps.

In particular, data will be reviewed by the Sponsor for identification of the following events that would potentially contribute to a requirement to pause/stop the study.

- Any deaths, regardless of causality
- Any drug-related SAEs
- Two or more participants in the same dose group/cohort experience non-serious severe AEs ( $\geq$ Grade 3) considered at least possibly drug-related
- Additional criteria specified in Section 7.1

#### **10.1.6. Dissemination of Clinical Study Data**

- The key design elements of this protocol and results summaries will be posted on [www.ClinicalTrials.gov](http://www.ClinicalTrials.gov) and/or GSK Study Register in compliance with applicable regulations/GSK policy. GSK will aim to register protocols summaries prior to study start and target results summaries submission within 12 months of primary/ study completion date (adult populations). Where external regulations require earlier disclosure, GSK will follow those timelines.
- Where required by regulation, summaries will also be posted on applicable national or regional clinical study registers.

- Where required by applicable regulatory requirements, an investigator signatory will be identified for the approval of the study report, and provided reasonable access to statistical tables, figures, and relevant reports. GSK will also provide the investigator with the full summary of the study results, including a summary of trial results understandable to laypersons. The investigator is encouraged to share the layperson summary of results with the study participants, as appropriate. The full study report will be made available upon request, after decision on marketing authorization by regulatory authorities.
- Where required by regulation, the names of the sponsor signatory and investigator signatory will be made public.
- GSK will provide the investigator with the randomization codes and participant-level line listings for their site only after completion of the full statistical analysis.
- GSK intends to make anonymized participant-level data from this study available to external researchers for scientific analyses or to conduct further research that can help advance medical science or improve patient care. This helps ensure the data provided by study participants are used to maximum effect in the creation of knowledge and understanding. Data will be shared with researchers in a non-identifying way, and appropriate measures will be taken to protect PI; these measures will comply with data protection and privacy laws that apply.

#### **10.1.7. Data Quality Assurance**

- All participant data relating to the study will be recorded on printed or electronic CRF unless transmitted to the sponsor or designee electronically (e.g., laboratory data). The investigator is responsible for verifying that data entries are accurate and correct by physically or electronically signing the CRF.
- The investigator must maintain accurate documentation (source data) that supports the information entered in the CRF. Quality tolerance limits will be pre-defined in the trial master file to identify systematic issues that can impact participant safety and/or reliability of study results. These pre-defined parameters will be monitored during and at the end of the study and all deviations from the quality tolerance limits and remedial actions taken will be summarized in the clinical study report.
- The investigator must permit study-related monitoring, audits, IRB/IEC review, and regulatory agency inspections and provide direct access to source data documents.
- Monitoring details describing strategy including definition of study critical data items and processes (e.g., risk-based initiatives in operations and quality such as Risk Management and Mitigation Strategies and Analytical Risk-Based Monitoring), methods, responsibilities and requirements, including handling of noncompliance issues and monitoring techniques (central, remote, or on-site monitoring) are provided in the Monitoring Plan.

- The sponsor or designee is responsible for the data management of this study including quality checking of the data. Detailed information about study data collection and management process including systems used can be found in the study Data Management Plan.
- The sponsor assumes accountability for actions delegated to other individuals (e.g., Contract Research Organizations).
- Records and documents, including signed ICF, pertaining to the conduct of this study must be retained by the investigator for 25 years from the issue of the final CSR/ equivalent summary unless local regulations or institutional policies require a longer retention period. No records may be destroyed during the retention period without the written approval of the sponsor. No records may be transferred to another location or party without written notification to the sponsor.

#### **10.1.8. Source Documents**

- Source documents provide evidence for the existence of the participant and substantiate the integrity of the data collected. Source documents are filed at the investigator's site.
- Data reported on the CRF or entered in the eCRF that are transcribed from source documents must be consistent with the source documents or the discrepancies must be explained. The investigator may need to request previous medical records or transfer records, depending on the study. Also, current medical records must be available.
- Definition of what constitutes source data and its origin can be found in the source data acknowledgment.
- The investigator must maintain accurate documentation (source data) that supports the information entered in the CRF.
- Study monitors will perform ongoing source data verification to confirm that data entered into the CRF by authorized site personnel are accurate, complete, and verifiable from source documents; that the safety and rights of participants are being protected; and that the study is being conducted in accordance with the currently approved protocol and any other study agreements, ICH GCP, and all applicable regulatory requirements.

#### **10.1.9. Study and Site Start and Closure**

##### **First Act of Recruitment**

The study start date is the date on which the clinical study will be open for recruitment of participants.

## Study/Site Termination

GSK or designee reserves the right to close the study site or terminate the study at any time for any reason at the sole discretion of GSK. Study sites will be closed upon study completion. A study site is considered closed when all required documents and study supplies have been collected and a study-site closure visit has been performed.

The investigator may initiate study-site closure at any time, provided there is reasonable cause and sufficient notice is given in advance of the intended termination.

Reasons for the early closure of a study site by the sponsor or investigator may include but are not limited to:

For study termination:

- Discontinuation of further study intervention development

For site termination:

- Failure of the investigator to comply with the protocol, the requirements of the IRB/IEC or local health authorities, the sponsor's procedures, or GCP guidelines
- Inadequate or no recruitment of participants (evaluated after a reasonable amount of time) by the investigator
- If the study is prematurely terminated or suspended, the sponsor shall promptly inform the investigators, the IECs/IRBs, the regulatory authorities, and any contract research organization(s) used in the study of the reason for termination or suspension, as specified by the applicable regulatory requirements. The investigator shall promptly inform the subject and should assure appropriate participant therapy and/or follow-up

### 10.1.10. Publication Policy

- The results of this study may be published or presented at scientific meetings. If this is foreseen, the investigator agrees to submit all manuscripts or abstracts to the sponsor before submission. This allows the sponsor to protect proprietary information and to provide comments.
- The sponsor will comply with the requirements for publication of study results. In accordance with standard editorial and ethical practice, the sponsor will generally support publication of multicenter studies only in their entirety and not as individual site data. In this case, a coordinating investigator will be designated by mutual agreement.
- GSK seeks to publish medically or scientifically significant results in searchable peer-reviewed scientific literature within 18 months from LSLV. We follow International Committee of Medical Journal Editors standards for authorship and use Good Publications practices to guide our publications.

## 10.2. Appendix 2: Clinical Laboratory Tests

[figure not shown]
The tests detailed in [Table 14](#) will be performed by the local or central laboratories as documented in the Laboratory Manual.

Protocol-specific requirements for inclusion or exclusion of participants are detailed in [Section 5](#) of the protocol.

Additional tests may be performed at any time during the study as determined necessary by the investigator or required by local regulations.

**Table 14 Protocol-Required Tests**

CCI

CCI

CCI

### 10.3. Appendix 3: AEs and SAEs: Definitions and Procedures for Recording, Evaluating, Follow-up, and Reporting

#### 10.3.1. Definition of AE

AE Definition

An AE is any untoward medical occurrence in a clinical study participant, temporally associated with the use of a study intervention, whether or not considered related to the study intervention.

NOTE: An AE can therefore be any unfavorable and unintended sign (including an abnormal laboratory finding), symptom, or disease (new or exacerbated) temporally associated with the use of a study intervention.

Events Meeting the AE Definition

Any abnormal laboratory test results (hematology, clinical chemistry, or urinalysis) or other safety assessments (e.g., ECG, radiological scans, vital signs measurements), including those that worsen from baseline, considered clinically significant in the medical and scientific judgment of the investigator (i.e., not related to progression of underlying disease).

Exacerbation of a chronic or intermittent pre-existing condition including either an increase in frequency and/or intensity of the condition.

New conditions detected or diagnosed after study intervention administration even though it may have been present before the start of the study.

Signs, symptoms, or the clinical sequelae of a suspected intervention- intervention interaction.

Signs, symptoms, or the clinical sequelae of a suspected overdose of either study intervention or a concomitant medication. Overdose per se will not be reported as an AE/SAE unless it is an intentional overdose taken with possible suicidal/self-harming intent. Such overdoses should be reported regardless of sequelae.

Events that occur as a result of protocol-mandated procedures (i.e., invasive procedures, modification of participant's previous therapeutic regimen).

"Lack of efficacy" or "failure of expected pharmacological action" per se will not be reported as an AE or SAE. Such instances will be captured in the efficacy assessments. However, the signs, symptoms, and/or clinical sequelae resulting from lack of efficacy will be reported as AE or SAE if they fulfill the definition of an AE or SAE.

Events NOT Meeting the AE Definition

 
Any clinically significant abnormal laboratory findings or other abnormal safety assessments which are associated with the underlying disease, unless judged by the investigator to be more severe than expected for the participant's condition.
 
The disease/disorder being studied or expected progression, signs, or symptoms of the disease/disorder being studied, unless more severe than expected for the participant's condition.
 
Medical or surgical procedure (e.g., endoscopy, appendectomy): the condition that leads to the procedure is the AE.
 
Situations in which an untoward medical occurrence did not occur (social and/or convenience admission to a hospital).
 
Anticipated day-to-day fluctuations of pre-existing disease(s) or condition(s) present or detected at the start of the study that do not worsen.
 
Hospitalization for elective treatment of a pre-existing condition (known or diagnosed before signing the informed consent) that did not worsen from baseline.
 

### 10.3.2. Definition of SAE

If an event is not an AE per definition above, then it cannot be an SAE even if serious conditions are met (e.g., hospitalization for signs/symptoms of the disease under study, death due to progression of disease).

An SAE is defined as any serious adverse event that, at any dose:
a. Results in death
b. Is life-threatening  The term 'life-threatening' in the definition of 'serious' refers to an event in which the participant was at risk of death at the time of the event. It does not refer to an event, which hypothetically might have caused death, if it were more severe.
c. Requires inpatient hospitalization or prolongation of existing hospitalization 
 
In general, hospitalization signifies that the participant has been admitted (usually involving at least an overnight stay) at the hospital or emergency ward for observation and/or treatment that would not have been appropriate in the physician's office or outpatient setting. Complications that occur during hospitalization are AE. If a complication prolongs hospitalization or fulfills any other serious criteria, the event is serious. When in doubt as to whether
 

An SAE is defined as any serious adverse event that, at any dose:

“hospitalization” occurred or was necessary, the AE should be considered serious.
 
 
Hospitalization for elective treatment of a pre-existing condition that did not worsen from baseline is not considered an AE.
 

d. Results in persistent or significant disability/incapacity
 
 
The term disability means a substantial disruption of a person’s ability to conduct normal life functions.
 
This definition is not intended to include experiences of relatively minor medical significance such as uncomplicated headache, nausea, vomiting, diarrhea, influenza, and accidental trauma (e.g. sprained ankle) which may interfere with or prevent everyday life functions but do not constitute a substantial disruption.
 

e. Is a congenital anomaly/birth defect
f. Abnormal pregnancy outcomes (e.g., spontaneous abortion, fetal death, stillbirth, congenital anomalies, ectopic pregnancy)

g. Other situations:
 
 
Possible Hy’s Law case: ALT <math>\geq 3</math>x ULN AND total bilirubin <math>\geq 2</math>x ULN (for participants with known Gilbert’s syndrome these criteria only apply if total bilirubin <math>\geq 2</math>xULN, and direct bilirubin <math>\geq 2</math>xULN and at least doubled from baseline value) or INR <math>> 1.5</math> must be reported as SAE.
 
Medical or scientific judgment should be exercised by the investigator in deciding whether SAE reporting is appropriate in other situations such as significant medical events that may jeopardize the participant or may require medical or surgical intervention to prevent one of the other outcomes listed in the above definition. These events should usually be considered serious. 
 
Examples of such events include invasive or malignant cancers, intensive treatment for allergic bronchospasm, blood dyscrasias, convulsions, or development of intervention dependency or intervention abuse.
 
 
 

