- Closure or termination of the study

In the event of any of the following, ongoing dosing will be halted for all participants in a dose group/cohort:

- Two or more participants in the same dose group/cohort experience non-serious severe AEs considered at least possibly related to the administration of GSK3965193. These two AEs do not need to be within the same system, organ, or class.
- Any participant experiences an SAE considered at least possibly related to the administration of GSK3965193. The dosing will be temporarily halted, and no further participants will be dosed until a full safety review of the study has taken place. Relevant reporting and discussion with the GSK medical monitor, relevant GSK personnel, and with the CA and Institutional Review Board (IRB)/Independent Ethics Committees (IEC) will then take place prior to any resumption of dosing, which may also include the evaluation of lower doses. If following an internal safety review, it is appropriate to restart the trial, a substantial amendment will be submitted to the Regulatory Agencies and ethic committees. The trial will not restart until the amendment has been approved by the Agency(s) and ethic committee(s).

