## 10.6. Appendix 6: Liver Safety: Required Actions and Follow-up Assessments

### Parts 1, 2, and 3 (GSK3965193 monotherapy) Liver chemistry stopping criteria and required follow up assessments

Liver chemistry stopping criteria and required follow up assessments

CCI

Required actions, monitoring and follow-up to assess causality of liver event	
Actions and monitoring	Follow-up to assess causality of liver event

 
• Immediately discontinue study treatment
 
• Report the event to GSK within 24 hours
 
• Complete the liver event CRF, and complete an SAE data collection tool if the event also meets the criteria for an SAE
 
• Perform liver event follow up assessments
 
• Monitor the subject until liver chemistries resolve, stabilise, or return to within baseline (see MONITORING below)
 
 
MONITORING: If ALT ≥ 3xULN AND bilirubin ≥ 2xULN or INR > 1.5
 
 
• Repeat liver chemistries (include ALT, AST, alkaline phosphatase, total bilirubin and INR) and perform liver event follow up assessments within 24 hrs
 
• Monitor participants twice weekly until liver chemistries resolve, stabilise or return to within baseline
 
• A specialist or hepatology consultation is recommended
 
	
 
• Viral hepatitis serology
 
• Anti-nuclear antibody, anti-smooth muscle antibody, Type 1 anti-liver kidney microsomal antibodies, and quantitative total immunoglobulin G (IgG) or gamma globulins.
 
• Obtain INR and recheck with each liver chemistry assessment until the transaminases values show downward trend
 
• Obtain blood sample for PK analysis, within 48 hours of last dose
 
• Serum GGT, CPK, LDH and serum albumin.
 
• Fractionate bilirubin, if total bilirubin ≥ 2xULN
 
• Obtain complete blood count with differential to assess eosinophilia
 
• Record the appearance or worsening of clinical symptoms of liver injury, or hypersensitivity, on the liver event CRF
 
• Record use of concomitant medications on the concomitant medications report form including acetaminophen, herbal remedies, recreational drugs and other over the counter
 

Liver Chemistry Stopping Criteria	

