
For all other stopping criteria (bilirubin <math>\leq 2xULN</math> and INR <math>< 1.5</math>):
 
 
Repeat liver chemistries (include ALT, AST, alkaline phosphatase, bilirubin and INR) and perform liver event follow up assessments within 24-72 hrs
 
Monitor participants weekly until liver chemistries reduce to <math>< 3xULN</math> for ALT or return to or remain within baseline or normal limits.
 
 
RESTART or RECHALLENGE
 
 
Do not restart or rechallenge participant with study intervention since not allowed per protocol; continue participant in the study for any protocol-specified follow-up assessments.
 
	
medications.
 
 
Record alcohol use on the liver event alcohol intake case report form
 
 
If ALT <math>\geq 3xULN</math> AND bilirubin <math>\geq 2xULN</math> or INR <math>> 1.5</math> obtain the following in addition to the assessments listed above:
 
 
Serum acetaminophen adduct assay should be conducted (where available) to assess potential acetaminophen contribution to liver injury.
 
Liver imaging (ultrasound, magnetic resonance, or computed tomography) to evaluate liver disease, complete liver imaging forms.
 
Liver biopsy may be considered and discussed with local specialist if available: 
 
In patients when serology raises the possibility of AIH.
 
In patients when suspected DILI progresses or fails to resolve on withdrawal of study intervention.
 
In patients with acute or chronic atypical presentation.
 
 
 
If liver biopsy conducted, then complete liver biopsy form.
 

- Serum bilirubin fractionation should be performed if testing is available. If serum bilirubin fractionation is not immediately available, discontinue study treatment for that subject if ALT  $\geq 3xULN$  and bilirubin  $\geq 2xULN$ . Additionally, if serum bilirubin fractionation testing is unavailable, record presence of detectable urinary bilirubin on dipstick, indicating direct bilirubin elevations and suggesting liver injury.

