- All events of ALT  $\geq 3xULN$  and total bilirubin  $\geq 2xULN$  (for participants with known Gilbert's syndrome these criteria only apply if total bilirubin  $\geq 2xULN$ , and direct bilirubin  $\geq 2xULN$  and at least doubled from baseline value) or ALT  $\geq 3xULN$  and INR  $> 1.5$ , which may indicate severe liver injury (possible 'Hy's Law'), must be reported as an SAE (excluding studies of hepatic impairment or cirrhosis); the INR threshold value stated will not apply to participants receiving anticoagulants.
- New or worsening symptoms believed to be related to liver injury (such as fatigue, nausea, vomiting, right upper quadrant pain or tenderness, or jaundice) or believed to be related to hypersensitivity (such as fever, rash or eosinophilia).
- Includes: Hepatitis A IgM antibody; Hepatitis B surface antigen, Hepatitis B virus DNA load and Hepatitis B Core Antibody (IgM); Hepatitis C RNA; Hepatitis D antibody, Cytomegalovirus IgM antibody; Epstein-Barr viral capsid antigen IgM antibody (or if unavailable, obtain heterophile antibody or monospot testing); Hepatitis E IgM antibody
- PK sample may not be required for participants known to be receiving placebo or non-GSK comparator treatments. Record the date/time of the PK blood sample draw and the date/time of the last dose of study treatment prior to PK blood sample draw on the CRF. If the date or time of the last dose is unclear, provide the subject's best approximation. If the date/time of the last dose cannot be approximated OR a PK sample cannot be collected in the time period indicated above, do not obtain a PK sample. Instructions for sample handling and shipping are in the Laboratory Manual.

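### The possible-Hy's-Law SAE rule in Protocol 10.3.2(g) is ungrouped and, on one reading, conflicts with the 10.6 footnote; separately, the two liver follow-up rows in 10.6 are not complements at their boundary

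*Protocol*

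**What the plan says.** **SAE rule, Protocol 10.3.2(g).** Under the label of a possible Hy's Law case, the sentence joins ALT ≥3xULN and total bilirubin ≥2xULN with AND, inserts a Gilbert qualifier in parentheses, and closes "at least doubled from baseline value) or INR > 1.5 must be reported as SAE". The closing parenthesis ends the Gilbert qualifier and does not group the conditions. The INR limb carries no ALT condition of its own and no exemption. The definition is not limited to any study part.

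**SAE footnote, Protocol 10.6.** The footnote to the liver table writes ALT ≥3xULN in both limbs, once with bilirubin and once with INR, describes such events as ones "which may indicate severe liver injury (possible 'Hy's Law'), must be reported as an SAE", and adds that "the INR threshold value stated will not apply to participants receiving anticoagulants". The table it belongs to is headed "Parts 1, 2, and 3 (GSK3965193 monotherapy) Liver chemistry stopping criteria and required follow up assessments".

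**Follow-up rows, same table.** The urgent row (repeat tests within 24 hours, then twice-weekly monitoring) opens "If ALT ≥ 3xULN AND bilirubin ≥ 2xULN or INR > 1.5". The other row (repeat in 24 to 72 hours, then weekly) opens "For all other stopping criteria (bilirubin \leq 2xULN and INR < 1.5". The trigger for additional assessments repeats the ungrouped form: "or INR > 1.5 obtain the following in addition to the assessments listed above". These entries govern follow-up; within 10.6 only the footnote is an SAE rule.

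**The concern.** An SAE definition should give one answer for one set of laboratory values. Here a site that works from 10.3.2(g) and a site that works from the 10.6 footnote can classify the same INR result differently, depending on how the first sentence is parsed. SAE incidence is a primary endpoint in every part (Protocol Section 3). A drug-related SAE also feeds the pause and stop reviews in Sections 7.1 and 10.1.5.1. The visible SAP text contains no possible-Hy's-Law rule of its own that would settle the question at analysis.

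The ambiguity matters most where nothing corrects it. The Part 3 bepirovirsen and Part 4 text in Sections 7.1.1 and 10.6 has no visible possible-Hy's-Law SAE statement. Section 2.3.1 expects ALT flares there, and the follow-up procedures require INR when a liver criterion is met.

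The follow-up rows raise a smaller, separate problem. They are meant to divide the stopping cases into two classes, but their inequality signs do not do so.

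**Working it through.** No sample size, power or alpha is involved. The check is logical, so the passages are set side by side.

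**Step 1: the SAE rule.** Let A = ALT ≥3xULN, B = total bilirubin ≥2xULN, C = INR >1.5. The Gilbert qualifier is the same in both places and is set aside.

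- 10.3.2(g), literal: (A and B) or C
- 10.3.2(g), grouped: A and (B or C)
- 10.6 footnote: (A and B) or (A and C), which equals A and (B or C)

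The literal form therefore differs from the footnote exactly when C holds and A does not. On a grid of ALT {1, 3}xULN, bilirubin {1, 2, 2.5}xULN and INR {1.2, 1.5, 1.6}, which has 2 × 3 × 3 = 18 cells:

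- literal against footnote: 3 cells disagree (ALT 1xULN, INR 1.6, any of the three bilirubin values); each is an SAE under 10.3.2(g) and not under the footnote;
- grouped against footnote: 0 cells disagree. The anticoagulant exemption is then the only remaining difference.

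**Step 2: who is covered.** The footnote sits in a table for Parts 1, 2 and Part 3 GSK3965193 monotherapy. Parts 1 and 2 are complete (Sections 2.2 and 4.2). For Part 3 bepirovirsen and Part 4, the visible text leaves 10.3.2(g) alone. The body of Table 8 is redacted, so this holds for the visible text only.

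**Step 3: the follow-up rows.** The urgent row is bilirubin ≥2xULN or INR >1.5. Its complement is bilirubin <2xULN and INR ≤1.5. The printed second row is bilirubin ≤2xULN and INR <1.5, so both equality cases are placed wrongly for a complement. With ALT ≥3xULN the printed brackets give:

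| Bilirubin (xULN) | INR 1.2 | INR 1.5 | INR 1.6 |
|---|---|---|---|
| 1 | weekly row | **neither** | urgent row |
| 2 | **both** | urgent row | urgent row |
| 2.5 | urgent row | urgent row | urgent row |

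Of these 9 cells, 7 fall in one row, 1 in neither and 1 in both. Because A is true throughout, the result is the same on either grouping. Cells with ALT below 3xULN are left out: the stopping criteria that bring a participant into this table are redacted, so it cannot be seen whether such a participant would enter it.

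**The case against.** The strongest reply on the SAE rule is that its label, a possible Hy's Law case, points to the grouped reading, which agrees with the footnote. Section 10.3.2 also says that an event that is not an AE cannot be an SAE, and Section 10.3.1 makes a laboratory abnormality an AE only if the investigator judges it clinically significant. This stands. A reader might infer that the protocol makes an isolated INR above 1.5 an SAE, but the text supports only an ambiguity that conflicts with the footnote on one of two readings.

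The missing anticoagulant exemption has little reach. Exclusion 42 bars people with chronic hepatitis B who require anticoagulation, Section 6.8.2 bars its regular use during bepirovirsen, and exclusion 46(c) bars INR above 1.25 at entry. That also stands.

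On the follow-up rows, INR of exactly 1.5 does belong to the urgent row once ALT ≥3xULN and bilirubin ≥2xULN are met. The second row is also worded as a residual class, and some readers would sweep unassigned cases into it. But then its bracket contradicts its own opening words, and the overlap at bilirubin 2xULN remains. The problem is confined to Part 3 GSK3965193 monotherapy, because Section 7.1.1 sets twice-weekly monitoring for anyone meeting a Table 8 criterion in Part 3 bepirovirsen or Part 4.

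**Conclusion.** Two wording defects stand, and both should be reconciled.

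1. The SAE rule in 10.3.2(g) is ambiguous. It conflicts with the 10.6 footnote for any participant with INR above 1.5 and ALT below 3xULN if read literally, and for none if grouped, apart from the anticoagulant exemption. In the visible text it is the only such rule for Part 3 bepirovirsen and Part 4.
2. In Part 3 GSK3965193 monotherapy the follow-up rows leave one boundary case unassigned and assign another twice.

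Three stronger inferences are not supported. First, an INR result cannot by itself halt a cohort: the halt in Section 7.1 applies when "Any participant experiences an SAE considered at least possibly related to the administration of GSK3965193", so a causality judgement is also needed. Second, nobody at the boundary is left without follow-up: the table's unconditional actions still require immediate discontinuation, follow-up assessments, and monitoring until liver chemistries resolve, stabilise or return to baseline. Only the repeat window and the frequency are contradictory. Third, no frequency can be given for these cases, because the documents contain no distribution of INR in participants with a liver event.

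The conclusion rests on the visible text. The redacted stopping criteria and Table 8 could narrow it.

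**What to change.** Reconcile Section 10.3.2(g), the two follow-up rows and the additional-assessments trigger in 10.6, and the 10.6 footnote.

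- State the possible-Hy's-Law rule once, with explicit brackets around the bilirubin and INR limbs and with the Gilbert and anticoagulant exceptions attached. Cite that single statement in 10.3.2(g), in the 10.6 table, and in the Part 3 bepirovirsen and Part 4 text.
- Rewrite the two 10.6 follow-up rows as exact complements, so that each combination of bilirubin and INR, including the equality cases, falls in one row only.

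Which grouping, thresholds and monitoring intervals apply is for the sponsor to decide. The cost is protocol wording: no new assessment, no change to data collection and no additional participants.
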